3.5 Physician Participation

It is our hope that all medical oncologists that see patients with early stage breast cancer will participate so that the study captures broad clinical practice at all participating sites. There is no recruitment target for physician participation.

As described above, during months 4-6 and 10-12 of the study, physicians will receive ONE questionnaire for EACH patient that would meet the eligibility criteria for Oncotype DX ® testing. There are two versions of the physician's questionnaire (Pre-Intervention at 4-6 months and Post-Intervention at 10-12 months). This questionnaire consists of 8-9 questions and should take less than 5 minutes to complete. The questionnaire will be identified with the patient Study ID but will not record the physician's name. There are no risks to the physician bin completing the questionnaire. The study will not collect any data on individual physicians' practice patterns but instead _on each centre's practice as a whole. Completion of the questionnaire constitutes implied consent. A physician can also refuse to complete a questionnaire for a specific patient.

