3.7 Study Outcomes

Primary Endpoint: The primary outcome will be the proportion of patients for which Oncotype DX ® is ordered, defined as the number of patients with Oncotype DX ® orders divided by the number of patients eligible for Oncotype DX ® testing.

Secondary Endpoints:

Frequency and type of chemotherapy used will be collected from the patient's electronic medical record as will timing to start chemotherapy, radiation therapy and endocrine therapy. Prognostic risk scores, including Magee formulae, Gage and Tennessee equations will be calculated using patient and tumour characteristics. These scores will also be compared with Oncotype DX ® results when performed. Physician questionnaire results will be used to assess physician comfort when making systemic therapy decisions.

Economic analysis:

We will conduct a cost analysis and compare total health system costs before and after the model implementation from the Ontario government's perspective.

The cost components will include Oncotype DX cost (C\$4380), adjuvant chemotherapy cost and other health services costs. We assume that the PREDICT 2.1 tool is readily available at no cost. The cost associated with other health services among patients who receive and those who do not receive adjuvant chemotherapy (including cost of cancer clinic, in-patient services, physician billing, chemotherapy, endocrine therapy, supportive drug, home care, in-patient and emergency department costs) [26] will be obtained from a concurrent cohort study and Canadian sources. Based on this analysis, we will then extrapolate the cost findings to the entire population of Ontario to report the financial implications of our intervention to Cancer Care Ontario.

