4.0 STATISTICAL ANALYSIS

The primary analysis will be based on a hierarchical logistic regression analysis, with time period (pre-intervention versus post-intervention) as the primary covariate of interest. For this model, patient characteristics are considered nested within treating physician, which is nested within treatment centre. Adjustments will be performed for baseline characteristics. From our survey, it was evident that there was significant variability between centres (and between physicians) for ordering Oncotype DX. Data from Ottawa shows that approximately 15% of approximately 600 patients treated by 8 physicians have this test performed. In contrast, Kingston (5 physicians) sees around 200 eligible patients a year and Oncotype DX is ordered for around 65% of these patients,

Thunder Bay (3 physicians) sees around 70 patients a year and also tests around 65% of eligible patients, and Newmarket (3 physicians) sees around 130 eligible patients a year and Oncotype DX is ordered for around 75% of these patients. Windsor (3 physicians) and Kitchener (4 physicians) both see around 150 patients per year and orders Oncotype DX testing on 90% of eligible patients. Given concerns that use of hierarchical clusters may not sufficiently account for the substantial variability between sites, analyses will also be conducted by site, grouped by baseline rate of testing (i.e. Kingston, Thunder Bay and Newmarket will be combined, as will Windsor and Kitchener; Ottawa will be a separate group on its own). A similar analysis will be performed using hierarchical logistic regression. In addition, key supportive analyses will also be performed using a two-sample chi-square test within each site separately, comparing the change in proportion of patients for which Oncotype DX is ordered for each physician (i.e. post-intervention proportion – pre-intervention proportion for physician A, B, C, ...).

Analyses of secondary endpoints will be performed globally across all sites combined, and for each site individually. The chi-square test or Wilcoxon rank sum test will be used as appropriate for categorical or continuous endpoints respectively. Results will be presented using tables and figures, and exact confidence intervals will be constructed for outcomes of interest. Bootstrapping may be used for estimation purposes if required. All tests will be two-sided and statistical significance will be defined at the $\alpha=0.05$ level.

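### Comfort ratings repeat within about 26 physicians but are tested as independent, so the before/after p-value does not have its stated 5% level and can err in either direction

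*Combined protocol and SAP*

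**What the plan says.** Comfort appears under the secondary endpoints in section 3.7: "Physician questionnaire results will be used to assess physician comfort when making systemic therapy decisions". For secondary endpoints, section 4.0 says: "The chi-square test or Wilcoxon rank sum test will be used as appropriate for categorical or continuous endpoints respectively". These tests are to be run over all sites combined and for each site, two-sided at 0.05. Questionnaire data are not excepted.

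Section 3.5 sets out how the ratings arise. In months 4-6 and again in months 10-12, "physicians will receive ONE questionnaire for EACH patient that would meet the eligibility criteria for Oncotype DX ® testing". It adds: "A physician can also refuse to complete a questionnaire for a specific patient".

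Nesting of patients within physician and centre is specified in section 4.0 for the primary ordering model and for the similar analysis by site group, but not for secondary endpoints. Bootstrapping is optional, for estimation, with no mention of clusters. Section 3.5 says the form carries the patient's study number and not the physician's name. Section 3.8 says the data are not linked to the treating physician.

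**The concern.** A physician who completes a dozen forms in a window brings the same rating habits to each one. Chi-square and rank sum tests count those forms as separate, unrelated observations. They also ignore that largely the same physicians answer in both windows, which is the natural basis for a before/after comparison.

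Two kinds of error follow. If each physician's habits are stable and volumes are equal, the physician effect cancels and the test is too cautious. If physicians respond differently to the teaching, or if the mix of who returns forms changes between windows, the test is too liberal. In the second case a change in who is answering can look like a change in comfort. Sections 3.1 and 3.6 say the questionnaire is meant to inform the knowledge mobilisation strategy, so a misleading comfort result would have a use beyond the paper.

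**Working it through.** **No plan figure to reproduce.** The plan gives no power, ICC or effect size for comfort. The power figures in section 5.0 concern test ordering. They reproduce (continuity-corrected n of 301, 150 and 185 per period, against 300, 150 and 185) but do not bear on this point.

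**Inputs from the documents.**
- Physicians (section 4.0): "Data from Ottawa shows that approximately 15% of approximately 600 patients treated by 8 physicians have this test performed"; "Kingston (5 physicians) sees around 200 eligible patients a year"; "Thunder Bay (3 physicians) sees around 70 patients a year"; "Newmarket (3 physicians) sees around 130 eligible patients a year"; Windsor 3 and Kitchener 4. Total 8 + 5 + 3 + 3 + 3 + 4 = 26.
- Patients per six months (section 5.0): 300 + 75 + 75 + 75 + 35 + 75 = 635, so 635 / 2 = 317.5 forms per three-month window at full response. I take Grand River in section 5.0 to be Kitchener in section 4.0. The annual volumes in section 4.0 give (600 + 200 + 70 + 130 + 150 + 150) / 4 = 325, so the differences between the sections (for example Kingston) hardly matter here.
- Forms per physician per window: Ottawa 150/8 = 18.8; Newmarket and Windsor 37.5/3 = 12.5; Kitchener 37.5/4 = 9.4; Kingston 37.5/5 = 7.5; Thunder Bay 17.5/3 = 5.8.

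**Assumptions.** Five-level item; ICC 0.1, 0.3 or 0.5; no true average change. Where used: physician-specific change with SD s = 0.3 of the rating SD, and volumes varying between windows with coefficient of variation c = 0.5.

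**Formula.** With N = 317.5 forms per window and w the share of forms from each physician,

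Σw² = (150²/8 + 37.5²/3 + 37.5²/3 + 37.5²/5 + 17.5²/3 + 37.5²/4) / 317.5² = 4484.9 / 100806 = 0.0445, and NΣw² = 14.13.

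Let R be the true variance of the before/after difference divided by the variance the test assumes (2/N).
- Equal volumes, stable physicians: R = 1 − ICC.
- Volumes varying by chance (Poisson) add ICC, which brings R back to 1.
- Further volume variation adds ICC × c² × NΣw² = ICC × 0.25 × 14.13 = 3.53 × ICC.
- Physician-specific change adds (s²/2) × NΣw² = 0.045 × 14.13 = 0.636.

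Type I error = 2[1 − Φ(1.96/√R)].

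| Setting | ICC 0.1 | ICC 0.3 | ICC 0.5 |
|---|---|---|---|
| Equal volumes, stable physicians | R 0.90, 3.9% | R 0.70, 1.9% | R 0.50, 0.6% |
| Chance volumes, stable physicians | R 1.00, 5.0% | R 1.00, 5.0% | R 1.00, 5.0% |
| Equal volumes, change SD 0.3 | R 1.54, 11.4% | R 1.34, 9.0% | R 1.14, 6.6% |
| Chance volumes, change SD 0.3 | R 1.64, 12.5% | R 1.64, 12.5% | R 1.64, 12.5% |
| Chance volumes plus CV 0.5, stable | R 1.35, 9.2% | R 2.06, 17.2% | R 2.77, 23.9% |
| Chance volumes plus CV 0.5, change SD 0.3 | R 1.99, 16.5% | R 2.70, 23.3% | R 3.40, 28.8% |

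**Simulation of the rank sum test on a five-level score.** The pattern is the same: about 1-4% in the first row; 5.0%, 4.9% and 4.8% in the second; about 6-14% over the third and fourth; 8.4%, 14.4% and 22.5% with volume CV 0.5 and stable physicians; up to about 27% in the last. The closed form runs slightly high at the top, as it treats the rating as continuous and the window totals as fixed.

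**Second parameterisation.** Let a physician's effect correlate only partly between windows (correlation ρ). With equal volumes, R = (1 − ICC) + ICC(1 − ρ) × 14.13. ICC 0.2 and ρ 0.8 give 0.80 + 0.04 × 14.13 = 1.37, or 9.3%. ICC 0.3 and ρ 0.5 give 0.70 + 0.15 × 14.13 = 2.82, or 24%.

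**Comparator.** A paired analysis of each physician's mean change (signed-rank or t-test) stayed between about 3.5% and 6% in every simulated setting.

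**The case against.** The strongest reply is that repeated rating alone does not inflate error in this design. That is correct. The same physicians answer in both windows, so stable habits cancel, and with chance-only variation in volume the rank sum test is close to nominal. A reader might infer that the test is bound to produce false positives, in the range of 6-22% for instance. The documents do not support that: they give no ICC, volume variation or physician-specific change, and some reasonable values give less than 5%.

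A reader might also take comfort to be a fixed trait of the physician. Sections 3.4 and 3.5 describe one rating per patient, about the recommendation for that patient, so the ICC is below 1 and could be small.

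It can be said that no comfort p-value is expressly planned. Section 3.7 names no test, section 3.6 does not list comfort among the outcomes that PREDICT availability may affect, and the two questionnaire versions differ. But section 3.7 places comfort under secondary endpoints, and section 4.0 assigns tests to these without exception.

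The promise of caution over secondary endpoints, given after section 4.0's tests, concerns multiplicity. It does not correct a standard error. The privacy objection carries some weight: with three physicians at a site, a code is not fully anonymous, and sections 3.5 and 3.8 commit to centre-level data without physician linkage. Yet section 4.0 already nests by physician and compares ordering physician by physician, so the primary analysis needs the same code.

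**Conclusion.** The point holds as a validity defect of unknown direction. The planned p-value for comfort assumes an independence that the design does not have, so it cannot be read at 0.05. Over an ICC of 0.1 to 0.5, the true level runs from about 1% to about 27%. Values above 5% need physicians to differ in their change, or volumes or response to swing beyond chance. The lower end is also a cost: with stable volumes and a common shift, simulated power at ICC 0.5 was 67% for the rank sum test against 77% for the paired analysis.

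The range rests on the assumed ICC, change SD, volume variation and five-level item; the questionnaire itself is not in the documents available. The figure of 26 covers six named sites of a planned 6-8, with no physician recruitment target. The point concerns a secondary endpoint and says nothing against the primary ordering model. It should be corrected before the forms are issued, because without a physician code they cannot be grouped reliably afterwards.

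**What to change.** 1. In section 4.0, replace the chi-square and rank sum tests for comfort with a within-physician analysis across all sites. Use either an ordinal or linear mixed model with a physician random intercept and a physician-specific period effect, with a small-sample correction, or a signed-rank test on each physician's mean post-minus-pre rating.
2. Report site-level comfort descriptively where there are few physicians. The smallest two-sided signed-rank p-value with n physicians is 2/2ⁿ: 0.25 for three, 0.125 for four and 0.0625 for five. Of the named sites, only Ottawa could reach 0.05.
3. Put a coded, non-name physician number on each form, and amend sections 3.5 and 3.8 so that they agree with the physician nesting in section 4.0.
4. Report forms issued and returned per coded physician in each window, so that a change in who answers can be seen.

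The cost is SAP wording, one field on a form already in use, and a change to the statement that data are not linked to the physician, which may need ethics notification. If physicians hardly differ, some power is lost: at ICC 0.1, 54% for the paired analysis against 65% for the rank sum test in simulation.

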3.3 Study Procedures

Each site will have a different process for determining eligibility. Research staff at each site will be confirming Oncotype DX ® eligibility from pathology reports and will be working with New Patient booking staff (or similar) to get weekly/daily clinic lists of new patients whose tumors meet eligibly for Oncotype DX ® testing.

Patient tumours at each site will enter study screening when a complete pathology report is received. Once a patient tumour is deemed eligible, it is given a Study ID number. Pathology data is collected by study staff. At all points of the study, patients with eligible tumours will meet with their treating physician to discuss the individualised testing and treatment plan that is best for them.

Once the physician meets with the patient, we will also collect the chemotherapy treatment plan details.

After 3 months of activation, physicians will start completing a questionnaire for each new patient with an eligible tumour. Delaying the questionnaires for the first 3 months is to prevent bias.

After 6 months of activation, the physicians will receive a teaching session (Intervention) consisting of PowerPoint slides which will present an updated review on the benefits and limitations of Oncotype DX and PREDICT testing.

After this teaching session, study staff at each site will be using the pathology data to run the PREDICT tool for each patient and will provide the results to each physician prior to his/her meeting with each patient. Again after 3 months, we will re-introduce the physician questionnaire for the last 3 months of the study.

In summary:

Month 1 to 3: pathology and chemo data collected, NO physician questionnaire

Month 4 to 6: pathology and chemo data collected, PLUS physician questionnaire

Intervention teaching after 6 months of study activation

Month 7 to 9: pathology and chemo data collected, PREDICT 2.1 tool used, NO physician questionnaire

Month 10 to 12: pathology and chemo data collected, PREDICT 2.1 tool used, PLUS physician questionnaire

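### The cost analysis lists no cost for delivering the intervention (staff-run PREDICT and teaching), which on its own tilts the before-after comparison slightly in the intervention's favour

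*Combined protocol and SAP*

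**What the plan says.** Section 3.7 (Economic analysis) plans to "compare total health system costs before and after the model implementation from the Ontario government's perspective". The component list gives the Oncotype DX unit price and continues "4380), adjuvant chemotherapy cost and other health services costs". The last of these is then described as "The cost associated with other health services among patients who receive and those who do not receive adjuvant chemotherapy", that is, patient care split by chemotherapy receipt. On PREDICT the section says only "We assume that the PREDICT 2.1 tool is readily available at no cost". Having done this, "we will then extrapolate the cost findings to the entire population of Ontario", and the result goes to the provincial cancer agency as the financial implications of the intervention.

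Section 3.3 describes what changes at month 6. First, "the physicians will receive a teaching session (Intervention) consisting of PowerPoint slides". After that, "study staff at each site will be using the pathology data to run the PREDICT tool for each patient", and the result reaches the physician before the consultation. Section 3.4 adds that the result is attached to each chart. The same section lets physicians use PREDICT themselves in the first six months, but staff do not supply results then. Section 3.6 names total health system costs among the secondary objectives.

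**The concern.** The website is free in both periods, so its price does not distinguish them. What distinguishes them is staff running and filing PREDICT for each eligible patient, and the teaching session. These are the elements for which section 3.7 lists no cost. A payer adopting the approach would have to resource them in some form.

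The two sides also scale differently. Staff time is spent on every eligible patient, whereas Oncotype DX savings come only from tests not ordered. The omitted amount therefore stays roughly fixed per patient while the saving shrinks with the effect. More patients would not remove the shift, and the extrapolation would carry it to the provincial figure.

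**Working it through.** **Plan's own figures.** The documents state no expected saving and no delivery cost, so there is no cost figure to reproduce. The section 5.0 effects can be checked. A two-proportion calculation with continuity correction (80% power, two-sided 0.05) needs 301, 150 and 185 patients per period for the three site groups, against 300, 150 and 185 from the stated volumes. For 500 versus 500 and 50% falling to 40.1% (odds ratio 0.67), power is 88.2%, consistent with the claim of over 80%.

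**Step 1: Oncotype DX saving per eligible patient.** Inputs: six-month volumes and baseline ordering rates from section 5.0; C$4380 per test from section 3.7. For each site, post-period odds = OR × p/(1 − p), converted back to a proportion; tests averted = n × (p − p_post). Totals use unrounded values.

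| Site | n | Baseline | Averted, OR 0.50 | Averted, OR 0.67 | Averted, OR 0.80 |
|---|---|---|---|---|---|
| Ottawa | 300 | 15% | 20.68 | 13.28 | 7.89 |
| Newmarket | 75 | 75% | 11.25 | 6.17 | 3.31 |
| Windsor | 75 | 90% | 6.14 | 3.17 | 1.65 |
| Kingston | 75 | 65% | 12.64 | 7.17 | 3.92 |
| Thunder Bay | 35 | 65% | 5.90 | 3.35 | 1.83 |
| Grand River | 75 | 90% | 6.14 | 3.17 | 1.65 |
| Total | 635 | 48.5% | 62.74 | 36.30 | 20.24 |

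Saving per eligible patient = averted × 4380 / 635:

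- OR 0.50: 62.74 × 4380 / 635 = C$433
- OR 0.67: 36.30 × 4380 / 635 = C$250
- OR 0.80: 20.24 × 4380 / 635 = C$140

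If OR 0.67 is instead applied to a single pooled rate of 50%, the saving is (0.500 − 0.4012) × 4380 = C$433. That this equals the site-by-site figure at OR 0.50 is a coincidence. The site-by-site saving at 0.67 is lower because centres at 15% and 90% have less room to fall in absolute terms.

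**Step 2: staff time.** Assumption, not in the documents: C$10 to C$30 per eligible patient for running PREDICT and filing the result. For scale, 15 minutes at C$40 per hour is C$10 and 30 minutes at C$60 per hour is C$30.

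- OR 0.50: 10/433 to 30/433 = 2% to 7%
- OR 0.67: 10/250 to 30/250 = 4% to 12%
- OR 0.80: 10/140 to 30/140 = 7% to 21%

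**Step 3: adding teaching.** Section 4.0 gives 8 + 5 + 3 + 3 + 3 + 4 = 26 physicians. Hours and rates are again assumptions, and the cost is spread over the 500 post-period patients of section 5.0.

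| Case | Staff time per patient | Teaching per patient | Sum | Share of C$250 | Share of C$433 |
|---|---|---|---|---|---|
| Low: 5 min at C$30/h; 1 h at C$100 | 2.50 | 26 × 100/500 = 5.20 | C$7.70 | 3% | 2% |
| Middle: 15 min at C$40/h; 1 h at C$200 | 10.00 | 26 × 200/500 = 10.40 | C$20.40 | 8% | 5% |
| High: 30 min at C$60/h; 2 h at C$300 | 30.00 | 26 × 600/500 = 31.20 | C$61.20 | 24% | 14% |

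**Step 4: break-even.** Delivery would cancel the Oncotype DX saving only if ordering fell by less than 7.70/4380 = 0.2 to 61.20/4380 = 1.4 percentage points. The volume-weighted falls in step 1 are 62.74/635 = 9.9, 36.30/635 = 5.7 and 20.24/635 = 3.2 points.

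**The case against.** The zero-cost sentence prices the tool, which is indeed free. A reader might infer that the plan declares the whole intervention free; it does not. Delivery is left out by silence, and a list introduced as what the costs will include need not be exhaustive. That stands, but the other-services item is spelled out as patient care, so an analyst following the text would add no delivery cost.

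A reader might also infer that net savings are overstated. That presumes a saving. The documents forecast none, and chemotherapy and other care could move the total either way; if the total rises, the omission understates a net cost. Only the direction of the shift from this one item is established. Section 2.0 says Oncotype DX adds to local pathology workload, and section 3.7 does not list that either. Omitting it would work against the intervention, so the net effect of all unlisted costs is unknown.

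It would be wrong to count pathology screening and data collection, since both take place throughout the twelve months. Only running PREDICT and delivering the result is extra, and physicians' own use of the tool before month 6 is allowed. Nor does the plan judge savings per averted test: it compares total costs, and C$4380 is only a unit price.

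Finally, the work is done by research staff. The documents do not say who would do it in routine practice, so a trial time log is only a guide to the routine cost. This is a reason to show results both ways rather than to omit the cost.

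**Conclusion.** The concern holds in a limited form. As written, the plan leaves out a positive cost that arises only after implementation, and on its own this moves both the before-after comparison and the Ontario extrapolation towards the intervention. At the odds reduction of about 50% that section 5.0 calls clinically important, staff time is probably 2-7% of the Oncotype DX saving; at 0.67 it is 4-12%, and more if the effect is weaker. These shares rest on assumed unit costs, on section 5.0 volumes and rates with a common odds ratio across sites, and on a denominator of Oncotype DX savings alone rather than total cost. The issue is minor: it touches one secondary economic analysis and leaves the primary endpoint untouched.

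**What to change.** In section 3.7, keep PREDICT 2.1 itself at zero and add a post-period component for delivering the intervention:

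- Staff minutes to run PREDICT and file the result, logged for a sample of patients at each site and multiplied by the pay rate.
- Teaching hours (physicians attending and the presenter) as a one-off cost, not one that recurs with each patient in the extrapolation.
- Nothing for pathology screening or data collection, which occur in both periods.

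Report the cost comparison and the Ontario extrapolation with and without this component, and say whether it is in scope for the government perspective. The cost is a short time log by staff already in place and one extra line in the analysis. The log should be kept during the post-intervention months, because minutes are hard to recover afterwards. The downside is a slightly less favourable cost result.
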